8.1 Specification of safety parameters

8.2 Methods and times for the assessment, recording and analysis of safety parameters

8.3 Procedures for reporting for the registration and reporting of adverse events and intercurrent diseases

8.4 Type and duration of subjects following adverse events

9. statistical analysis

9.1 statistical analysis

Continuous variables will be summarized using the DS \pm mean. Categorical variables are represented using frequencies and percentages. For the comparison between responders and non-responders, the Student's 2-code t-test or the Wilcoxon test for continuous variables will be used. The Chi-square test or the Fisher test will be used for categorical variables.

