In women and patients with stable coronary artery disease, in antiplatelet therapy with aspirin, high platelet reactivity (HAPR) or resistance to aspirin has been described, which is associated with unfavorable clinical outcomes. A study conducted by Jesurum et al, suggested that subjects with migraine have a higher prevalence of HAPR than healthy subjects or patients with stable coronary artery disease being treated with aspirin 325 mg. However, the clinical implications of HAPR in subjects with emicrania and PFO require further investigation of analysis for the high risk of cerebral stroke and myocardial infarction and highlight the need to prescribe preventive antiplatelet therapy early.

Protocol number

NCT03521193

In addition, the extent of the right-left shunt as assessed and measured at the transcranial Doppler also increases progressively from the migraine-free control groups, to the migraineranics without aura and in those with aura¹⁷.

Recent studies have shown that a prominent Eustachian valve and a Chiari network, as an embryonic residue in the right atrium, are more often detectable in migraine patients with aura (100% in migraine with aura vs 55% in non-migraines)^{19,20} and this could explain the increase in dx-sin shunt. In addition, an analysis of the anatomy of the interatrial septal (SIA) showed the presence of SIA aneurysm in 13% of patients with migraine compared to 1.9% of control subjects ($p=0.05$)²¹. In addition, among migraine patients, SIA aneurysm was predominantly observed in subjects with aura (28%) compared to those without aura (3.6%)²¹.

Rational

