The premium (Prospective, Randomized Investigation to Evaluate Incidence of Headache Reduction in Subjects With Migraine and PFO Using the AMPLATZER PFO Occluder to Medical Management) study hypothesis was based on the possible significant reduction in the frequency of migraine attacks with and without aura after percutaneous correction of PFO and broad dx-sin shunt in patients symptomatic for migraine from 6 to 14 days/month and not responsive to drug therapies. The primary endpoint of the study was to reduce the frequency of migraine attacks (with or without aura) by at least 50%; the proportion of patients with headache reduction was superimposable in the PFO correction group (38.5%) and in that addressed to medical therapy (32%), $p=0.32$. With regard to secondary endpoints, there was a significant reduction in the number of migraine days/month after CORRECTION of PFO compared to the control group (-3.4 ± 4.4 days versus -2.0 ± 5.0 days ($p = 0.025$)). No difference was observed in the percentage of patients who achieved a 75% reduction > migraine attacks while a very significant difference was observed with regard to subjects who experienced a complete regression of migraine episodes: 8.5% (10/117) in the PFO correction group vs 1.0% (1/103) in the medical therapy group ($p=0.01$). Among these patient responders, 6 were symptomatic for migraine with aura while the other 4 were migraines with isolated episodes of aura.

It could be speculated that the etiological mechanism of headache in patients not subjected to PFO closure could be the activation of platelets inside the tunnel, the overlap between septum primum and secundum, of the patent foramen ovale. This segment, which may be characterized by a potential flow turbulence between the two septa, could lead to platelet activation, especially in the presence of SIA aneurysm. In a small group of patients with migraine, resistance to aspirin has been documented in 24% of subjects, suggesting platelet hyper-reactivity.

Clopidogrel and aspirin are more effective than aspirin alone in reducing headache, exacerbated after percutaneous correction of PFO in the first follow-up period²⁴ to demonstrate that platelet microaggregates may be responsible for post-closure migraine of PFO and may play a central role in the genesis of headache.

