In women and patients with stable coronary artery disease, in antiplatelet therapy with aspirin, high platelet reactivity (HAPR) or resistance to aspirin has been described and is associated with adverse clinical outcomes. A study conducted by Jesurum et al, suggested that subjects with migraine have a higher prevalence of HAPR than healthy subjects or patients with stable coronary artery disease being treated with aspirin 325 mg. However, the clinical implications of HAPR in subjects with migraine and PFO require further investigation of analysis for the high risk of cerebral stroke and myocardial infarction and the need to prescribe early prevention therapy.

A PFO with dx-sin shunt should require a neurological substrate susceptible and vulnerable to some substance that by-passes the pulmonary circle and induces headache. The endothelium of the

Protocol number

NCT03521193

pulmonary circle has significant metabolic activity. The lung in fact metabolizes, activates or inactivates many compounds including vasoactive amines and other humoral substances²⁵. Prostaglandins E1, E2 and F2 are completely removed from the bloodstream; serotonin is removed between 85% and 95%; 70% of angiotensin I is converted to angiotensin II, and 80% of bradykinin is inactivated²⁶. It is not known whether these substances may increase the susceptibility of the brain to stimulate environmental or intrinsic triggers capable of triggering migraine

Objectives and aims of the study

The aim of the study is to verify whether vasoactive/inflammatory substances together with increased platelet reactivity may play a key role in the onset of migraine and in its maintenance even after correction of PFO. The morphological and anatomical characteristics of the oval fossa will also be analyzed in order to identify elements that can correlate with increased platelet reactivity and predict a clear benefit in the control of migraine symptoms after correction of PFO. The analysis will also be extended to the evaluation of differences between female and male sex.

4. Study design

1. 4.1 Primary and secondary outcomes

Primary outcomes:

Evaluation of the % regression of migraine episodes with aura in relation to platelet reactivity in migraine patients, with and without aura, carriers of PFO, together with the dosage of PGE1, PGE2, serotonin and cytokines in order to identify potential predictive markers of beneficial effect of PFO correction on migraine symptoms.

Secondary outcomes

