5.3 Criteria for withdrawal

5.4 Informed consent

It is the responsibility of the researcher to obtain written informed consent from the participants before inclusion in the study, after a full explanation of the nature, objectives and risks inherent in participation in the study. The methods of processing personal data and clinical information obtained will also be explained to each participant; the participants in the study will sign the consent to the processing of personal data. It will also be emphasized that participation in the study is voluntary and it will be possible to interrupt it at any time or request at any time the elimination of any biological information or material obtained for research purposes.

6 Treatment of patients

1. 6.1 Treatment/Procedures and evaluations planned during the study

The study, which will take place at the [REDACTED], will be divided into two phases, described below.

Step 1: Screening of symptomatic PFO patients for migraine with aura initiated percutaneous PFO correction and clinical follow-up.

Estimated time: 24 months

This phase of the study aims to test the hypothesis that the population of subjects with PFO and indication to percutaneous correction of the defect, when symptomatic for migraine with or without aura, can be characterized as responders or non-responders with regression of the migraine symptomatology / aura.

The identification of symptomatic patients for migraine, after preliminary neurological evaluation, will be accompanied by a classification of migraine according to the severity scale of migraine sec. Anzola (Table 1). This evaluation will be repeated after PFO correction and outpatient clinical follow-up at a distance of 6 and 12 months, together with the execution of color-Doppler TT echocardiogram. This last examination will characterize the correct positioning of the PFO occlusive device and the presence/absence of residual inter-atrial shunt dx-sin.

TABLE 1. Migraine Severity Score

Intensity
0=No pain
1=Moderate (does not interfere with the performance of daily activities)
2=Severe (interferes with the performance of daily activities)
3=Inbearable (requires enticing)
Duration

Protocol number

NCT03521193

0=No pain

1=<6 hours

2=6–12 hours

3=>12 hours

Frequency

0=No pain

1=1–4/month

2=5–9/month

3=>10/month

Aura

0=No aura

OCCLUDER DEVICE FOR PFO

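### Section 9.1 compares responders with non-responders without accounting for aura, so septal aneurysm could look predictive of benefit when it adds nothing to aura status

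*Combined protocol and SAP*

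**What the plan says.** Section 9.1 gives the whole method in two sentences. "For the comparison between responders and non-responders", continuous variables get a two-sided t-test or a Wilcoxon test; for the rest, "The Chi-square test or the Fisher test will be used for categorical variables". It names no stratification, covariate or model.

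Section 6.1 (Step 1) puts both migraine types into this comparison: patients, "when symptomatic for migraine with or without aura, can be characterized as responders or non-responders".

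The objectives make anatomy a predictor under study: "The morphological and anatomical characteristics of the oval fossa will also be analyzed in order to identify elements" that, among other things, may "predict a clear benefit in the control of migraine symptoms after correction of PFO".

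The background gives the link between aura and anatomy: "SIA aneurysm was predominantly observed in subjects with aura (28%) compared to those without aura (3.6" per cent). It also says, without figures, that right-to-left shunt size rises from people without migraine, to migraine without aura, to migraine with aura.

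On response, the Rationale describes the ten complete responders in the closure arm of a cited randomised trial: "Among these patient responders, 6 were symptomatic for migraine with aura", and the other four had isolated aura episodes. The primary outcome in Section 4.1 concerns regression of episodes with aura, in patients with and without aura.

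Adjustment is mentioned only in Section 9.2. There, four unnamed confounders enter the correlation between change in the migraine severity score and five blood factors.

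**The concern.** A crude comparison of aneurysm between responders and non-responders is confounded by aura if aura is related to both. The relation to aneurysm is documented. The relation to response is plausible: every complete responder in the cited trial had some aura, and the primary outcome is worded around aura episodes.

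Aura is already known from the neurological evaluation. An anatomical marker therefore helps to select patients, or supports a mechanism, only if it tells the clinician something that aura does not. The tests in Section 9.1 cannot separate the two. The study could report septal aneurysm or a large shunt as a predictor of benefit when it is only a proxy for aura.

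**Working it through.** **The plan's own sample size.** For a correlation of 0.35, two-sided alpha 0.01 and 80% power, Fisher's z gives n = ((2.576 + 0.842) / atanh(0.35))² + 3 = 90.45, so 91. This agrees with the stated 92 to within one patient. Allowing for four covariates gives 95; at 92 the power is then 78.6%. The sample size is not affected by this point.

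**Inputs from the documents**
- Aneurysm prevalence: 28% with aura, 3.6% without (background).
- Aneurysm in all migraine patients of the same cited study: 13% (background). Implied aura share: (13 − 3.6) / (28 − 3.6) = 9.4 / 24.4 = 38.5%.
- Overall response: about 60% (Section 9.2).
- N = 92 (Section 9.2); test level 0.05 (Section 9.3).

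**Assumed:** the difference d in response rate between patients with and without aura, varied because the documents do not give it. Aneurysm has no effect within either aura group (true odds ratio 1).

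**Formulas,** with aura share p = 0.385:
- Response without aura r0 = 0.60 − p·d; with aura r1 = r0 + d.
- Aneurysm share in responders = [p·r1·0.28 + (1 − p)·r0·0.036] / 0.60.
- Aneurysm share in non-responders = [p·(1 − r1)·0.28 + (1 − p)·(1 − r0)·0.036] / 0.40.

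**Example, d = 30 points.** r0 = 0.60 − 0.385 × 0.30 = 0.4845 and r1 = 0.7845.
- Responders: (0.0846 + 0.0107) / 0.60 = 15.9%.
- Non-responders: (0.0232 + 0.0114) / 0.40 = 8.7%.
- The crude odds ratio is 1.99, although the true one is 1.

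**Simulated rejection rates** (N = 92, aura share 38.5%; 20,000 studies for chi-square and Mantel-Haenszel, 5,000 for Fisher):

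| d (points) | Crude odds ratio | Chi-square | Fisher | Mantel-Haenszel by aura |
|---|---|---|---|---|
| 0 | 1.00 | 4.8% | 3.5% | 4.8% |
| 10 | 1.24 | 5.9% | 4.4% | 5.2% |
| 20 | 1.56 | 8.9% | 7.0% | 5.1% |
| 30 | 1.99 | 15.9% | 13.2% | 4.9% |
| 40 | 2.61 | 25.3% | 21.1% | 4.6% |

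Repeat runs of the chi-square gave 5.7% at 10 points, 9.1% to 9.3% at 20, 15.2% to 15.7% at 30 and 24.8% to 25.8% at 40. The rounded figures are therefore about 6%, 9%, 15% and 25%.

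**Sensitivity to the aura share.** For the same differences of 10 to 40 points, chi-square rejection runs from 5.6% to 24.8% at a 50% share, and from 5.4% to 15.8% at a 70% share.

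**Which crude test applies.** The smallest expected cell with no association is 92 × 0.40 × 0.13 = 4.8. Fisher's test may well be the one used, so its column deserves equal weight.

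**Cases by stratum.** Expected aneurysms are 92 × 0.385 × 0.28 = 9.9 with aura and 92 × 0.615 × 0.036 = 2.0 without.

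**The case against.** The strongest objection is that the link between aura and response is not established. The Rationale gives numerators only: ten complete responders, with no count of treated patients by aura status. Complete regression occurred in 10 of 117 closures (8.5%), a much rarer outcome than the 60% assumed here. A reader might infer that the protocol's own figures tie aura to response; they only suggest it. This objection stands, and it makes the size of the bias a range. At a 10-point difference the distortion is negligible.

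Other tempting readings also go too far.

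- **Eustachian valve and Chiari network.** The quoted 100% versus 55% compares migraine with aura with people without migraine. It shows no contrast between migraine with and without aura, which is the one that matters here.
- **The severity score.** A reader might argue that its aura item gives patients with aura more points to lose. The available text of Table 1 breaks off after the first level of that item, and nothing says that responders are defined by this score.
- **The powered analysis.** The four confounders in Section 9.2 are unnamed and could include aura, and no passage links aura to the blood factors. That analysis is not shown to be affected. Equally, those confounders do not cover anatomy or the responder comparison, and Section 9.1 has no method that could use them.
- **A false predictor.** A feature that tracks response through aura does predict response marginally. The crude comparison answers that question legitimately; it cannot show prediction beyond aura.

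Finally, Section 5.1 lists aneurysm (with Chiari network or Eustachian valve) among its qualifying criteria, and many patients enter because of stroke or TIA. The 28% and 3.6% may not carry over to this cohort. That also stands.

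**Conclusion.** The point holds in conditional form. Section 9.1 has no analysis that can separate an anatomical predictor from aura, and for septal aneurysm the association with aura is large in the protocol's own background. For shunt size it is stated as a trend only.

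If response differs by aura, the crude test has an inflated chance of presenting aneurysm as informative beyond aura: slight at 10 points, roughly three times the nominal level at 30, and about five times at 40 with chi-square. This rests on 60% overall response, a 38.5% aura share, the background prevalences applying here, and an assumed aura difference in response that the documents do not supply.

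The issue concerns an additional aim, not the sample size or the blood-factor correlations. It should be corrected because the protection is nearly free whatever the true difference.

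**What to change.** - **Section 9.1:** keep the crude comparison. Beside it, test the anatomical predictors with adjustment for baseline aura (yes/no): a Mantel-Haenszel test or logistic model for septal aneurysm, and a logistic model for shunt size. State that any claim of prediction beyond aura rests on the adjusted result.
- **Section 9.2:** name baseline aura as one of the four confounders already budgeted.

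Do not plan separate aneurysm results within each aura group. With about two expected cases, the no-aura estimate would be uninformative.

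The cost is analysis wording and one degree of freedom. Aura status is already collected for the migraine severity score, and no change in sample size is needed. The adjusted aneurysm test will draw nearly all its information from patients with aura, so its precision will be limited; the report should say so.

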9.2 Calculation of the sample number

The sample size calculation is based on the 1-year primary endpoint. A value for the frequency of reaching the primary endpoint was placed around 60%, in accordance with the data reported in

Protocol number

NCT03521193

literature^{22, 27}. A sample of 92 patients was identified, necessary to obtain a potency of 80% able to detect as significant ($p < 0.01$, considering the Bonferroni correction for multiple tests) a correlation coefficient of 0.35 (adjusted for 4 confounding variables) between the variation of the migraine score sec. Anzola and any of the 5 factors (platelet reactivity, PGE1, PGE2, cytokines, serotonin) measured at baseline.

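### Section 9.1 names the Student t-test for responder groups likely to be unequal in size; if spreads also differ, its p-values and any pooled interval are miscalibrated, and Welch's test corrects this almost free (minor)

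*Combined protocol and SAP*

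**What the plan says.** Section 9.1 gives one rule for continuous variables. "For the comparison between responders and non-responders", it says, "the Student's 2-code t-test or the Wilcoxon test for continuous variables will be used" (2-code evidently means two-tailed). It does not mention the variance assumption, gives no rule for choosing between the two tests, and mentions no confidence interval.

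Section 9.2 supplies the only figure that bears on group sizes: "A value for the frequency of reaching the primary endpoint was placed around 60" per cent, with "A sample of 92 patients was identified". The p<0.01 level in 9.2 ("considering the Bonferroni correction for multiple tests") is attached to a different analysis: "a correlation coefficient of 0.35 (adjusted for 4 confounding variables"), "between the variation of the migraine score sec. Anzola and any of the 5 factors". Section 9.3 sets significance at 0.05 without restriction.

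No section gives the SD of any marker, overall or by response group.

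**The concern.** Responder status is observed after closure, so the design cannot balance the groups. With unequal groups, the pooled test estimates the standard error correctly only when the two variances are equal. If they differ, the pooled variance is weighted towards the larger group. The standard error is then too small when the smaller group is the more variable, and too large when the larger group is.

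At stake is the calibration of every responder versus non-responder comparison of a continuous variable that uses this test. In one direction, differences in means are called significant more often than stated. In the other, real differences are missed more often than necessary. Any confidence interval from the same pooled standard error is too narrow or too wide to match.

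**Working it through.** **The plan's own figure.** The 92 patients come from the adjusted correlation, not from the t-test. With f² = 0.35²/(1 − 0.35²) = 0.1225/0.8775 = 0.1396, one tested predictor plus four covariates (df1 = 1, df2 = N − 6), two-sided 0.01 and noncentrality f²(df1 + df2 + 1), power first reaches 80% at N = 92. The figure is reproduced and is not affected by what follows.

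**Inputs.**
- Total 92 and frequency 60% (section 9.2): 0.60 × 92 = 55.2, so about 55 responders and 37 non-responders. This is an inference; the plan does not state group sizes.
- Level 0.05 (section 9.3).
- SD ratio r = non-responder SD / responder SD: not in the documents. Assumed values are 1/2, 1/1.5, 1, 1.5 and 2, with normal data and equal means.

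**Large-sample formula.** With responder SD = 1, the true variance of the mean difference is V = 1/55 + r²/37. The pooled test uses, on average, about P = [(55 + 37r²)/92] × (1/55 + 1/37), where 1/55 + 1/37 = 0.04521. The actual level is about 2[1 − Φ(1.96/√(V/P))].

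- r = 1.5: V = 0.01818 + 0.06081 = 0.07899; P = 1.5027 × 0.04521 = 0.06794; √(V/P) = 1.078; 1.96/1.078 = 1.818; level 6.9%.
- r = 2: V = 0.12629; P = 2.2065 × 0.04521 = 0.09975; √(V/P) = 1.125; 1.96/1.125 = 1.742; level 8.2%.
- r = 1/1.5: V = 0.03019; P = 0.7766 × 0.04521 = 0.03511; √(V/P) = 0.927; 1.96/0.927 = 2.113; level 3.5%.
- r = 1/2: V = 0.02494; P = 0.6984 × 0.04521 = 0.03157; √(V/P) = 0.889; 1.96/0.889 = 2.205; level 2.7%.

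**Simulation**, 55 vs 37, nominal 0.05 (1,000,000 data sets per setting for the t-tests, 40,000 for Wilcoxon):

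| r | Student | Welch | Wilcoxon | Coverage of pooled 95% interval (100% − Student) |
|---|---|---|---|---|
| 1/2 | 2.9% | 5.0% | 4.2% | 97.1% |
| 1/1.5 | 3.5% | 5.0% | 4.5% | 96.5% |
| 1 | 5.0% | 5.0% | 5.0% | 95.0% |
| 1.5 | 7.0% | 5.0% | 6.2% | 93.0% |
| 2 | 8.3% | 5.0% | 7.7% | 91.7% |

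The simulation agrees with the formula. With a 46/46 split, Student stays between 5.0% and 5.2% even at ratios from 1/3 to 3, so the imbalance combined with unequal spread is the cause. The Wilcoxon alternative also drifts, though less.

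**Cost of Welch when SDs are equal.** At a standardised difference of 0.75, power is 93.6% against 93.7% for Student at the 0.05 level, and 81.0% against 81.3% at 0.01. Over differences from 0.5 to 0.8, the largest loss is about 0.2 points at 0.05 and about 0.4 points at 0.01 (57.4% against 57.7% at 0.6).

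**The case against.** Four points on the other side carry weight.

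1. **A marker unrelated to response is not affected.** If a baseline marker has nothing to do with response, its distribution, and so its spread, is the same in both groups, and Student holds its level. A reader might infer from the error rates above that false baseline markers would be declared at up to twice the stated rate. The documents do not support that. The rationale's hyper-reactive patients (aspirin resistance in 24% of a small migraine group) do not supply the mechanism either. Suppose such a subgroup existed only among non-responders, shifted by 2.62 SD. Its added variance is 0.24 × 0.76 × 2.62² = 1.25, so the SD ratio is √2.25 = 1.5. But the mean also moves, by 0.24 × 2.62 = 0.63 SD. That is a real association. This point stands, and it limits the concern to variables whose spread does differ with response.

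2. **The p<0.01 level.** A reader might also infer that the Bonferroni level in 9.2 governs this t-test. It is attached to the adjusted correlation with the Anzola score change; the general level in 9.3 is 0.05. The result is therefore stated at 0.05.

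3. **The size is assumed.** There are no SDs in the documents, the direction is unknown, and the 55/37 split rests on an endpoint frequency, with no responder threshold defined. This stands; the figures are conditional.

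4. **The text does not say equal variances.** Section 9.1 is terse and translated, and it also allows Wilcoxon. But Student without qualification ordinarily means the pooled test, and Wilcoxon is not a full remedy for unequal spread, as the table shows.

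**Conclusion.** The concern holds as a minor, conditional one. If the spread of a continuous variable differs between responders and non-responders, the test named in 9.1 misses the 0.05 level of 9.3 at about 55 vs 37. The rate is about 7% to 8% when the smaller group has 1.5 to 2 times the SD, and about 3.5% to 2.9% when the larger group does. Coverage of a pooled 95% interval is off by the same amounts, and for normal data that remains true when the means really differ. With equal spread there is no distortion.

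This rests on reading Student as the pooled form, on the inferred split, on normal data, and on assumed SD ratios. Nothing in the documents shows that spreads do differ. The sample size of 92 is untouched.

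**What to change.** In section 9.1, replace the Student test with the two-sided Welch t-test (unequal variances) for every responder versus non-responder comparison of a continuous variable, and report the confidence interval for the mean difference from the same test.

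The cost is a few words and one software option: no patients, no new data, and about 0.4 power points or less if the SDs turn out equal. The change does not settle other open matters in section 9, such as the undefined responder threshold, the unreconciled 0.01 and 0.05 levels, and the absence from 9.1 of the correlation analysis that 9.2 sizes.

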Cytofluorimetry studies will allow to characterize the state of platelet activation in terms of protein expression both on the cell surface and inside the cell. In particular, the expression of P-selectin, activated GpIIb/IIIa, Tissue Factor and Phosphatidylserine will be evaluated through the use of specific monoclonal antibodies. These analyses will be performed both in basal conditions and after *in vitro* activation with agonists such as ADP, thrombin and epinephrine. The same conditions will also be used for the evaluation of the presence of mixed aggregates, platelet-leukocytes, sensitive index of platelet activation.

PRP (Platelet-Rich Plasma), separated from the blood by centrifugation, will be used to perform platelet aggregation studies in response to different agonists such as ADP, collagen, thrombin, epinephrine and arachidonic acid.

The characterization of the circulating microvesicles will be performed on samples of Platelet-Free Plasma (PLP), by means of a multiparametric analysis performed using the new generation cytofluorimeters. In particular, not only the total number of microvesicles present in the sample will be considered, but a detailed phenotyping will be performed that will give information on the

Protocol number

NCT03521193

cellular derivation of the microvesicles, considering in particular those of platelet, leukocyte and endothelial origin.

Serum TXB₂ levels and urinary excretion of 11-dehydro-TXB₂ will be evaluated by mass spectrometry.

The levels of the inflammatory cytokines IL-1, IL-6, TNF α will be measured on plasma samples with enzyme immunoassay, while the levels of PGE₁, PGE₂ and serotonin will be dosed by HPLC method.

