9.3 Significance level to use

Statistical significance will be considered that obtained with a p value of 0.05.

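### The 92 patients and 80% power belong to a covariate-adjusted correlation at p<0.01, but section 9.1 prescribes only unadjusted responder versus non-responder tests

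*Combined protocol and SAP*

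**What the plan says.** **Section 9.2 (sample size).** The 92 patients give 80% power, at p<0.01 after a Bonferroni correction, to detect "a correlation coefficient of 0.35 (adjusted for 4 confounding variables) between the variation of the migraine score sec. Anzola". On the other side of that correlation, taken one at a time, stand the baseline markers, which the section describes as "any of the 5 factors (platelet reactivity, PGE1, PGE2, cytokines, serotonin) measured at baseline". The section also puts the frequency of reaching the one-year primary endpoint at around 60%. It does not name the four confounders.

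**Section 9.1 (analysis).** Apart from descriptive summaries, the only methods are two-group tests of responders against non-responders. For these, Student's "2-code t-test or the Wilcoxon test for continuous variables will be used", with chi-square or Fisher tests for categorical variables.

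**Section 9.3 (significance).** "Statistical significance will be considered that obtained with a p value of 0.05". It does not say whether this level applies per test or to the family of five.

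**Section 6.1 (procedures).** Step 1 says that patients "can be characterized as responders or non-responders with regression of the migraine symptomatology / aura", with no threshold. Phase 2 lists several measurements under single factor names: "The levels of the inflammatory cytokines IL-1, IL-6, TNF" alpha, and "platelet aggregation studies in response to different agonists such as ADP, collagen, thrombin, epinephrine and arachidonic acid". It adds four flow-cytometry markers, read at baseline and after agonists, and mixed platelet-leukocyte aggregates.

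**Sections 4.1 and 7.1 (outcomes).** Section 4.1 words the primary outcome as "Evaluation of the % regression of migraine episodes with aura in relation to platelet reactivity in migraine patients", which is not a change in Anzola score. Section 7.1 has endpoint headings with no text under them.

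**The concern.** The power statement and the analysis plan describe different analyses. The outcome is a score change in 9.2 and a dichotomy in 9.1. There are four adjustments in 9.2 and none in 9.1. The test level is 0.01 in 9.2 and 0.05 in 9.3.

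An analyst who follows 9.1 leaves out the confounders that 9.2 treats as necessary and cannot claim the 80%. An analyst who tries to follow 9.2 can infer the outcome and the test level, but must invent the covariates and choose a variable for platelet reactivity and for cytokines. In a single-centre observational study looking for predictive markers, those choices, and the responder cut, could be made after the data are seen. The Bonferroni divisor of five protects only if exactly five tests are run.

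**Working it through.** **1. Reproduce the 92.** Inputs from 9.2: r = 0.35, alpha 0.01, power 80%, k = 4 covariates. A two-sided test is assumed, because 9.2 does not say. By Fisher z:

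n = [(z for 1−alpha/2 + z for power) / atanh(r)]² + 3 + k

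- atanh(0.35) = 0.3654, and (2.576 + 0.842)/0.3654 squared = 87.45.
- k = 0: 87.45 + 3 = 90.5, so 91 patients.
- k = 4: 87.45 + 7 = 94.5, so 95 patients.
- Power at n = 92, k = 4: 0.3654 × √85 − 2.576 = 0.793, which gives 78.6%. Simulation gives 79.1%.
- A noncentral F test of one predictor with four covariates gives n = 88 for 80%, and 82.6% at 92.

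These variants bracket 92. One-sided 0.01 gives 79 (k = 0) or 83 (k = 4), and two-sided 0.05 gives 62 or 66. The plan's figure is therefore a two-sided correlation calculation at 0.01, and its arithmetic is sound.

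**2. Compare it with the analysis prescribed.**

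| | 9.2 | 9.1 and 9.3 |
|---|---|---|
| Outcome | Anzola score change | responder or not, undefined |
| Method | adjusted correlation | t-test, Wilcoxon, chi-square, Fisher |
| Covariates | four, unnamed | none |
| Level | 0.01 | 0.05 |

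**3. Illustrate the power of the 9.1 tests.** The documents do not fix this figure. Assumptions: the marker and the score change are bivariate normal, the best 60% are responders (55 against 37 of 92), and the unadjusted correlation is 0.35.

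- The cut is at −0.2533, where the normal density is 0.3863.
- Point-biserial correlation: 0.35 × 0.3863/√(0.6 × 0.4) = 0.276.
- Standardised difference: [0.35 × 0.3863/0.24]/√(1 − 0.276²) = 0.586.
- Noncentrality: 0.586 × √(55 × 37/92) = 2.757, with 90 degrees of freedom.

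| Test, n = 92 | Power at 0.01 | Power at 0.05 |
|---|---|---|
| t-test, noncentral t | 55% | 78% |
| t-test, simulated | 54% | 77% |
| Wilcoxon, simulated | 51% | 75% |

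At 0.01 the t-test has 38.6%, 70.4% and 83.7% power for unadjusted correlations of 0.30, 0.40 and 0.45. If the point-biserial correlation is itself 0.35 (latent correlation 0.35 × √0.24/0.3863 = 0.444), it has about 82%.

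**4. Number of tests (independence assumed).**

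- Five at 0.01: 1 − 0.99⁵ = 4.9% family-wise error.
- Seven at 0.01 (three cytokines counted separately): 1 − 0.99⁷ = 6.8%.
- Five at 0.05: 1 − 0.95⁵ = 22.6%.
- Seven at 0.05/7 with k = 4: critical value 2.690, power at 92 = 75%, and n for 80% = 93.40 + 7 = 100.4, so 101.
- Twelve at 0.05/12 with k = 4: power at 92 = 69%, and n for 80% = 102.89 + 7 = 109.9, so 110.

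**5. Cost of one more covariate.** With the baseline score as a fifth covariate, 0.3654 × √84 − 2.576 = 0.774, which gives 78.0% power.

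**The case against.** The strongest reply is that 9.1 never calls the responder comparison primary or exclusive. Section 9.2 already gives the outcome, the timing, the five factors, the number of adjustments and the level, so the powered analysis is misplaced and incomplete rather than replaced. That may well be what happened. It does not supply the four confounders, the responder cut or the variable behind each factor. The data collection sheet is not shown and may list candidate confounders, but a list of variables is not a model.

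Second, the 54% pairs the test of 9.1 with the level of 9.2. Read literally, 9.1 with 9.3 gives about 77%, close to 80%. This is correct and belongs beside the 54%, but that level gives up the multiplicity control on which 9.2 relies.

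Third, the illustration sets an unadjusted 0.35 against an adjusted 0.35, assumes normality for a score built from ordinal items, and reads the 60% endpoint frequency as a responder cut. All of this stands, so the figures show that a loss is plausible and do not measure it. Likewise, seven tests is a lower bound, because it still counts platelet reactivity as one variable.

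Fourth, a linear model is a choice for an ordinal composite. A rank-based partial correlation could be specified instead, provided that it is named in advance.

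Finally, one could grade the point lower because the study is exploratory and observational. However, it concerns the main analysis and the only justification for the sample size.

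**Conclusion.** The concern holds and must be fixed. The 80% at 92 patients describes an adjusted correlation at 0.01 that the analysis section does not contain, and it does not describe the unadjusted two-group tests that the section does contain. This follows from the text and needs no assumption.

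The size of the power loss is unknown. Under the stated assumptions the t-test at 0.01 runs from about 39% to 84% as the unadjusted correlation goes from 0.30 to 0.45, so some plausible cases show no loss. The severity rests on the missing model, the unnamed covariates and the undefined factor variables, not on those percentages. The 0.05 in 9.3 is compatible with being the family-wise level behind the 0.01, but it needs to say so.

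**What to change.** - **9.1:** make the powered analysis primary. For each of the five factors, fit a linear regression (partial correlation) of the 12-month change in Anzola score on the baseline factor, adjusted for the four confounders and tested at 0.01. Keep the responder comparisons as secondary and descriptive, with the cut defined.
- **Covariates:** name the four, check that the data collection sheet records them, and say whether the baseline score is one of them. As a fifth covariate it leaves about 78% power.
- **Factors:** name one platelet-reactivity measure, and one cytokine or cytokine composite, before the data are examined. Otherwise divide 0.05 by the actual number of tests and restate the power.
- **9.3:** state that 0.05 is the family-wise level and 0.01 the per-factor level.
- **4.1 and 7.1:** bring the primary outcome wording into line with the outcome analysed.
- **Alternative:** if the responder comparison is to be primary, define a responder and restate the power of that test at 92 patients.

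The cost is a protocol amendment, which section 18 makes subject to Ethics Committee approval, and a little analysis work. No extra patients are needed if one variable is named per factor, and no extra data if the confounders are already collected. If the three cytokines are tested separately with a single platelet measure, the choice is about 75% power at 92 patients or about 101 patients for 80%. Testing more platelet readings costs more.
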